Additionally, two randomised controlled trials (RCTs) have found beneficial effects of inhaled budesonide on recovery times in patients with symptomatic COVID-19^{14,15}, while RCTs investigating ciclesonide have found conflicting results, with one study finding shortened duration of viral shedding¹⁶ and two studies finding no statistically significant effect of ciclesonide on symptom resolution on day 7¹⁷ or time to symptom alleviation¹⁸. RCTs consequently suggested a strong protective effect of one inhaled ICS, budesonide, in patients with mild COVID-19.^{14,15} The conflicting results between the RCTs and observational studies may be a result of different study questions and populations, or biases affecting the observational studies.

The design of pharmacoepidemiologic studies in COVID-19 is complicated by the polyphasic nature of the disease, which means that different treatments may have different effects at different stages of the COVID-19 disease pathway from infection to hospitalisation and death.¹⁹ It can therefore be difficult to compare results between studies when there are differences in study design and differences in timing of drug administration, and the populations studied.¹⁹ However, the inconsistent findings may also be in part due to biases affecting the studies.

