Exposure will be prescription of ICS, which may be determined in a time-fixed or time-updated manner. Which method of exposure ascertainment will be chosen will be informed by the findings of the descriptive study of prescription patterns. For example, if we observe a significant increase in prescriptions for ICS at the start of the pandemic (March 2020) in the descriptive study, suggesting stockpiling occurred, it may be difficult to ascertain the end of an exposure period. While a time-updated approach would be more accurate and preferable in theory, a time-fixed exposure definition may be preferable if exposure periods cannot be estimated with confidence, for example due to stockpiling. The descriptive study will be completed before the start of the analyses of the comparative studies.

- **Time-fixed exposure:** prescription of ICS within 3 months before the cohort entry date (1st March 2020 for wave 1, 1st September 2020 for wave 2), and the comparator group as people who did not receive a prescription for ICS within the 3 months before the cohort entry date, but did receive a prescription for another inhaled medication for COPD or asthma. Patients can then not switch between exposure groups, even if they initiate ICS or their ICS exposure ends, analogous to an “intention to treat” approach.
- **Time-updated exposure:** ICS prescriptions in the year before the cohort entry date up until the end of follow-up will be used to ascertain exposure status throughout the follow-up time. Length of exposure for each prescription will be calculated by multiplying the quantity by any relevant dose information stored in the packtype variable and dividing by the value in the numeric daily dose variable. Where it is not possible to calculate the exposure period, the median prescription length for that drug might be imputed as the exposure duration.⁴² An allowable gap between the end of a calculated drug supply and receipt of a new prescription would be permitted, e.g. half a median exposure duration. Where one prescription is issued

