before the previous one is estimated to have been completely used, we will assume stockpiling occurred and assign the maximum total days of exposure possible with the combined prescriptions. Patients who switch treatment groups will be considered exposed to the active comparator/ICS group from the date of the switch, and those who discontinue treatment or switch to a treatment not under study will be censored at discontinuation or switch.

Patients will be considered exposed from the date the prescription was issued, as ICS have been shown to exert anti-inflammatory effects within hours of administration.⁴³

Outcomes

- SARS-CoV-2 infection, defined as a recorded positive test for SARS-CoV-2 in the primary care record sourced from the Second Generation Surveillance System (SGSS).
- hospitalisation with COVID-19, defined as admission to hospital with an ICD-10 code for COVID-19, ascertained using HES data.
- death with COVID-19, defined as death with an ICD-10 code for COVID-19 listed as an underlying or contributing cause of death in the ONS death registry.

Covariates

- demographic and lifestyle variables at baseline: age, sex, body mass index (BMI), smoking status, ethnicity, socioeconomic status (Index of Multiple Deprivation, IMD)
- ever-present comorbidities at baseline: chronic kidney disease, hypertension, heart failure, other heart diseases, diabetes, cancer, immunosuppression
- time-updated covariates: influenza vaccination within one year before the cohort entry date, pneumococcal vaccination within 5 years before the cohort entry date, vaccination against COVID-19 (wave 2 only)
- calendar time, COVID-19 prevalence figures (ONS)
- asthma cohort only: number of recorded asthma exacerbations (emergency department visit, hospitalisation or prescription of an oral corticosteroid for asthma⁴⁴) within 1 year before the cohort entry date
- COPD cohort only: number of recorded COPD exacerbations (defined using a validated algorithm⁴⁵) within 1 year before the cohort entry date.

O. Data analysis

Descriptive study:

Population-level measures of ICS use that will be determined per calendar month are:

- Number and proportion of incident and prevalent users over the course of follow-up for each calendar month:
 - Prevalent ICS exposure will include people with an ICS prescription recorded on any day during that month.

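### If exposure is time-updated, starting ICS exposure on the issue date with no lag can credit ICS with infections that were already acquired (objective 2a)

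*Protocol*

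**What the plan says.** Section N leaves the exposure definition open: "Exposure will be prescription of ICS, which may be determined in a time-fixed or time-updated manner". The descriptive study is to inform the choice. The protocol regards the time-updated form as better in principle, but says the time-fixed form may be the better choice if stockpiling makes exposure periods uncertain.

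In the time-updated form, "ICS prescriptions in the year before the cohort entry date up until the end of follow-up will be used to ascertain exposure status" throughout follow-up. Two rules fix when ICS exposure begins: "Patients will be considered exposed from the date the prescription was issued, as ICS have been shown to exert anti-inflammatory effects within hours", and "Patients who switch treatment groups will be considered exposed to the active comparator/ICS group from the date of the switch". Onset of action is the only reason given for the immediate start.

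In the time-fixed form, only prescriptions before cohort entry count: "Patients can then not switch between exposure groups, even if they initiate ICS or their ICS exposure ends".

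The outcome for objective 2a (item B.a in section D) is "SARS-CoV-2 infection, defined as a recorded positive test for SARS-CoV-2 in the primary care record".

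**The concern.** A test that is positive on a given day detects an infection acquired earlier. An ICS issued between the first symptoms and the test cannot have caused or prevented that infection, however fast it acts. What matters is why it was issued. In a patient with asthma or COPD, new cough or breathlessness from undiagnosed COVID-19 is a plausible reason to issue an inhaler. This is protopathic bias, a form of reverse causation.

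With no lag, the event moves from the comparator group to the ICS group while almost no person-time moves with it, so the HR is pushed upward. The section D objectives concern prevalent ICS use, and an ICS first issued days before the test is hardly that. The study exists to quantify biases in this literature, so a reverse-causation route in its own exposure definition deserves explicit treatment.

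**Working it through.** **1. Is it handled elsewhere in the protocol?**

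- Covariates (section N): none records acute respiratory symptoms. The exacerbation counts refer to the year before cohort entry. The covariates listed as time-updated are vaccinations.
- Time-updated propensity scores and confounders (sections O and Q): these can adjust only for what is measured. Even an updated asthma exacerbation count, built on emergency visits, admissions and oral corticosteroids, would miss a cough that led only to a new inhaler.
- Sensitivity analyses (section O): dose strata, no conditioning on test or admission, and adding coded cases without a test. None uses a lag.
- Quantitative bias analysis (section P): adherence and stockpiling, missed infections, selection, and severity of the underlying disease. Prescribing prompted by the infection is not named.

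**2. The protocol's own benchmark.** Table 1 (section K) follows from the Schoenfeld formula with two-sided α = 0.05, 80% power and an ICS share of 0.64. For HR 1.1:

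events = (1.960 + 0.842)² / [0.64 × 0.36 × (ln 1.1)²] ≈ 3,750; at an outcome probability of 0.5%, N = 750,027, as printed.

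All 77 cells reproduce, so the sample size is not in question. It supplies the yardstick: HR 1.1 in asthma and 1.2 in COPD for a positive test.

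**3. Expected wave 1 cases at a true HR of 1.00** (sections J and K)

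- Probability of a positive test: 295,134 / 56,550,000 = 0.522%.
- Asthma: 485,192 with ICS gives 2,532 cases; 755,632 − 485,192 = 270,440 without gives 1,411.
- COPD: 83,668 with ICS gives 437 cases; 225,472 − 83,668 = 141,804 without gives 740.

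**4. Effect of moving cases.** Let f be the share of comparator cases issued an ICS between symptoms and test, and q the ICS share. Person-time is treated as unchanged, because only days move:

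apparent HR = (1 + f(1 − q)/q) / (1 − f)

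Here (1 − q)/q is 270,440/485,192 = 0.557 in asthma and 141,804/83,668 = 1.695 in COPD. The documents give no value for f; the range is assumed.

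| f (assumed) | Asthma: cases moved | Asthma: HR | COPD: HR if counted as a switch | COPD: HR if censored, 1/(1 − f) |
|---|---|---|---|---|
| 1% | 14 | 1.02 | 1.03 | 1.01 |
| 5% | 71 | 1.08 | 1.14 | 1.05 |
| 10% | 141 | 1.17 | 1.30 | 1.11 |

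The last column is needed because section N censors a switch to a treatment not under study, and section L excludes patients already on LABA/LAMA plus ICS at entry. A COPD comparator who adds ICS to LABA/LAMA might therefore be censored. In that case the comparator loses the event but ICS does not gain it (shown before any censoring weights).

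**5. Share needed to reach the benchmark.** Solving for f: f = (HR − 1) / (HR + (1 − q)/q).

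- Asthma, HR 1.1: 0.1 / (1.1 + 0.557) = 6.0%, about 85 of 1,411 cases.
- COPD, HR 1.2, if counted as a switch: 0.2 / (1.2 + 1.695) = 6.9%, about 51 of 740 cases.

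**6. Sensitivity to comparator size.** Real comparators need another inhaled medication and must survive the exclusions. If the asthma comparator were half as large (assumed), (1 − q)/q = 0.279, and f = 5% or 10% gives 1.07 or 1.14.

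**The case against.** The strongest case against runs as follows.

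- **The point is conditional.** The time-fixed option is immune, and the protocol may well choose it, since it already names stockpiling in March and April 2020 as a threat. Even under time-updating, only comparator patients who start ICS during follow-up are affected; established users are exposed with or without a lag. This stands and limits the scope.
- **The size is assumed.** No document gives a rate of ICS issue for COVID-19 symptoms, and the comparator counts are too broad. On these counts, shares of 1% to 5% stay below an HR of 1.1 in asthma. This stands.
- **Other methods might absorb it.** Section D includes bias analysis for unmeasured or unknown confounders, and section P allows several biases to be modelled together. Both could take in this bias, but as written neither does.
- **Early ICS may truly affect later outcomes.** A reader might infer that the no-lag rule is equally wrong for hospitalisation and death. The documents do not support that. The Background states that "RCTs consequently suggested a strong protective effect of one inhaled ICS, budesonide, in patients with mild COVID-19", so an ICS issued at symptom onset could alter progression, and speed of action is then relevant. Symptom-driven prescribing may still confound those outcomes, but the argument that the drug came too late to matter applies to acquisition only.
- **The budesonide trials do not show what prescribers did.** A reader might also take them as evidence that ICS were issued for COVID-19 symptoms in wave 1. The reference list dates both reports 2021, after wave 1 ended on 31 August 2020.

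**Conclusion.** The point holds for objective 2a if the time-updated definition is used. The issue-date rule then lets ICS be credited with infections already acquired, the stated justification does not address this, and nothing in the protocol targets it. The direction is upward. The size is unknown: about 1.02 to 1.17 in asthma for assumed shares of 1% to 10%, with about 6% needed to mimic the stated detectable effect. These figures rest on a true HR of 1.00, negligible moved person-time, and feasibility counts that treat everyone without ICS as a comparator. In COPD the effect is smaller if adding ICS leads to censoring and larger if it counts as a switch; the text can be read either way.

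This does not show that the study's HR will be biased by any given amount. Nor does it justify making a lag the main analysis for hospitalisation or death, or redefining exposure in objectives 2b and 2c. Those steps would change the estimand and could remove a genuine early-treatment effect.

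**What to change.** If the time-updated definition is chosen:

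- **Objective 2a:** lag changes of exposure by a pre-specified period (for example 14 days), keeping the previous status during the lag. Report lag 0 and one longer lag as sensitivity analyses. If the lag is long enough to cover the prompted prescriptions, f becomes 0 and the apparent HR in the calculation above returns to 1.00.
- **Hospitalisation and death:** keep the planned definition and add a lagged analysis as a sensitivity analysis only.
- **COPD:** state whether adding ICS to LABA/LAMA counts, for the analysis, as a switch or as censoring.

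No new data are needed. The cost is that a few truly exposed days are assigned to the earlier status, and that the lag must be aligned with the censoring weights and the time-updated propensity scores, so it takes more than one line of code. If the time-fixed definition is chosen, no change is needed on this point.

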D. Aims, objectives, rationale

The aim of this study is to investigate the effects of ICS at different stages of the COVID-19 disease pathway (i.e., infection, hospitalisation, and death) among patients with asthma or COPD and apply methods of QBA to these effect estimates to account for potential biases arising in these estimates of association. The null hypothesis is that use of ICS has no effect on COVID-19-related outcomes.

Objectives

- A. To describe prescription patterns of ICS among patients with respiratory diseases before and during the COVID-19 pandemic.
- B. To investigate the association between prevalent ICS use and COVID-19 related outcomes among patients with respiratory diseases.
 - a. Estimate the association between prevalent ICS use and risk of having a positive SARS-CoV-2 test.
 - b. Estimate the association between prevalent ICS use and risk of hospitalization with COVID-19 among patients with a positive SARS-CoV-2 test.
 - c. Estimate the association between prevalent ICS use and risk of death among patients who were hospitalized with COVID-19.
- C. To develop approaches and apply methods of QBA to account for potential biases arising in these estimates of association.
 - a. Investigate impact of exposure misclassification (e.g., due to stockpiling of medication, patients not filling prescription or underascertainment of in-hospital medication use) on estimates from objective 2a, 2b, and 2c.
 - b. Quantify potential biases due to unmeasured or unknown confounders on estimates from objective 2a, 2b, and 2c.
 - c. Investigate impact of outcome misclassification (e.g., underascertainment of infections due to limited testing availability and non-random testing) on estimates from objective 2a.
 - d. Investigate impact of selection bias (e.g., non-random selection of individuals into a study) on estimates from objective 2b and 2c.

E. Outcomes

COVID-19 positive test result; hospitalisation with COVID-19; death with COVID-19, as defined in section N.

F. Study type

The overall study design is a historical cohort study.

G. Study design

Objective 1 will be a descriptive study with a population-level description of prescription patterns of ICS before and during the COVID-19 pandemic among patients with respiratory disease.

Objective 2 will be a hypothesis testing cohort study. The null hypothesis is that there is no association between ICS use and testing positive for COVID-19, hospitalisation for COVID-19 and death with COVID-19.

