For each cohort and each calendar month, the study population will consist of people who have a record of asthma or COPD. For the asthma cohorts, each monthly cohort will consist of those patients who, on the 15th of each month (the index date), had 1) their first asthma code on or before that date; and 2) did not have COPD on or before that date.³⁹ Correspondingly, for the COPD cohorts, each monthly cohort will consist of those patients who, on the 15th of each month, had 1) their first COPD code on or before that date; and 2) did not have asthma on or within 3 years before that date. To be included in a cohort, patients must have at least one year of follow-up in CPRD prior to the index date and have age and gender recorded in CPRD.

Comparative cohort studies

For the comparative cohort studies, the study population will consist of two separate, mutually exclusive disease cohorts, a COPD cohort and an asthma cohort, consisting of patients registered with GP practices meeting CPRD quality control standards. For each disease cohort (asthma and COPD), two cohorts will be created, one for the first wave of COVID-19 and one for the second, defined relative to a cohort entry date (1st March 2020 for wave 1, 1st September 2020 for wave 2), to make a total of four cohorts. To be included in a cohort, patients must have at least one year of follow-up in CPRD prior to the cohort entry date, be eligible for linkage to HES data, and have gender and age recorded in CPRD.

Asthma cohort⁴⁰

The asthma cohort will include all adults aged 18 and over with a recorded diagnosis of asthma defined as a record of asthma within 3 years prior to the cohort entry date. This method of identifying asthma has previously been validated in CPRD.⁴⁰ Code lists to identify asthma will be reviewed by a clinical expert before use.

Patients will be excluded if they have a record of COPD or any other chronic respiratory condition at any point before the cohort entry date, or a prescription of a LAMA but no ICS within 3 years before the cohort entry date, as this indicates possible COPD. Patients who received a prescription of nebulised medication within 1 year before the cohort entry date will also be excluded, as this indicates very severe asthma.

COPD cohort⁴¹

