The COPD cohort will include all adults aged 35 and over with a recorded diagnosis of COPD at any point before the cohort entry date.⁴¹ This method of identifying COPD has previously been validated in CPRD.⁴¹ Code lists to identify COPD will be reviewed by a clinical expert before use. To be included, patients must also have a record of current or former smoking in CPRD.

As in the asthma cohort, patients who have a record of other chronic respiratory conditions at any point before the cohort entry date will be excluded. People who use a leukotriene receptor antagonist (LTRA) within 3 years of the cohort entry date will be excluded as this indicates asthma, as will people who are prescribed a LABA/LAMA and ICS within 3 months before the cohort entry date, as this indicates severe COPD.

Censoring

For all cohorts, cohort exit will be defined as the first of either occurrence of the outcome (for each analysis), death, disenrollment from GP practice, the last date of data availability, or the end of the COVID-19 wave (31st August 2020 for wave 1, 30th April 2021 for wave 2).

M. Comparator groups

The study will use an active comparator group including all people with recorded asthma within 3 years or COPD at any point before the cohort entry date (1st March 2020 or 1st September 2020, respectively) who received a prescription for inhaled medication for asthma or COPD, but no ICS prescription.

The comparator group for the asthma cohort will be people who were not prescribed medication containing ICS and were prescribed a non-ICS inhaled medication for asthma. For the COPD cohort, the comparator group will include people who were not prescribed a medication containing ICS and were prescribed a LABA/LAMA separately or in combination for COPD. Exposures and exposure durations in the comparator group will be calculated in the same way as in the ICS-exposed group.

N. Exposures, outcomes and covariates

Exposure

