- Incident ICS exposure will be defined as a new ICS prescription with no prescription in the previous 6 months. Prevalent users will therefore also include incident users.
- The denominator will be all people with asthma or COPD in each month **Error!**

Reference source not found..

- Number of individual prescriptions per person per month (absolute number).
- Dosages prescribed: median or mean daily dose among those prescribed ICS for any given month.
- Discontinuation of ICS or date of treatment switch: number and proportion of people who have ≥ 6 months of no ICS-containing inhaler prescription.

This study will be descriptive. Results will be presented as absolute numbers and proportions as bar graphs.

The results from this study will inform the exposure definition that will be used in the comparative cohort study (see section on Exposure definitions). This study will be completed before starting the analyses for the subsequent comparative cohort studies.

Comparative cohort studies:

We will conduct descriptive analyses (frequency, percentages, mean [SD] and median [IQR]) to assess characteristics of the patients in each cohort, stratified by exposure group at baseline. Categorical variables will be compared using χ^2 tests. Continuous variables will be compared using t-tests for normally distributed variables and Mann-Whitney test for non-normally distributed variables. Time to each outcome will be presented using Kaplan-Meier plots using time in study as the time scale.

Propensity scores will be generated using logistic regression to estimate likelihood of ICS prescription based on baseline characteristics. All pre-specified covariates will be included in the logistic regression.

The association between ICS prescription and each outcome will be estimated using a Cox regression model to calculate hazard ratios and 95% CIs, using time in study as the time scale. Univariable models, models adjusted for age and sex, and propensity score weighted models will be presented. Schoenfeld residuals will be used to graphically assess the validity of the proportional hazards assumption. If the proportional hazards assumption is violated, we will use interaction terms between the exposure and time to describe any variations in the hazard ratio over time.

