Exposure misclassification may arise due to low adherence to inhaled medication for respiratory diseases⁴⁷⁻⁴⁹, and due to stockpiling of medication⁴⁷ at the beginning of the pandemic (March and April 2020). The descriptive cohort study (objective 1) will investigate prescription patterns and the potential extent of stockpiling during the pandemic. To adjust for potential exposure misclassification, we will calculate proxy measures for adherence (proportion of days covered or medication possession ratio) in the year before the COVID-19 pandemic (March 2019 – February 2020) and use these, together with data from literature and input from clinicians, to estimate adherence during the pandemic. Additionally, we are looking to obtain questionnaire data on adherence during the pandemic from the Optimum Patient Care Research Database (OPCRD). If this data is not obtained, or is not suitable for these purposes, we will estimate exposure misclassification using data from literature and input from clinicians.

In objective 2a, the outcome of SARS-CoV-2 infection may be misclassified as testing was conducted in a non-random manner. Especially in the first wave of COVID-19, testing was very limited, and therefore not all infections will have been ascertained. It is plausible that the probability of getting tested for SARS-CoV-2 was not equal among people prescribed ICS and those not prescribed ICS, resulting in differential misclassification of SARS-CoV-2 infection. We will use test data from CPRD and data from the ONS infection survey to estimate how many SARS-CoV-2 infections may have been missed in the respective study populations. We will work together with clinicians to create plausible bounds for sensitivity and specificity of the outcome classification.

Selection Bias:

Analyses that are restricted to people who received a positive test for SARS-CoV-2 or were hospitalised with COVID-19 may be vulnerable to selection bias. Potential differential misclassification of SARS-CoV-2 infections in objective 2a would result in selection bias in objective 2b, as selection into the study

population is conditional on a positive test for SARS-CoV-2. In order to adjust for selection bias, the bias parameters necessary are the selection probabilities S for each combination of exposure E and outcome D :

- Probability of being selected into the study conditional on being exposed and experiencing the outcome ($P(S|D=1, E=1)$),

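### Objectives 2b and 2c include patients from a later positive test or admission, but the only time zero the protocol defines is the start of the wave

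*Protocol*

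**What the plan says.** Section D (items a to c under B, called 2a to 2c elsewhere in the protocol) sets 2b as "risk of hospitalization with COVID-19 among patients with a positive SARS-CoV-2 test" and 2c as "risk of death among patients who were hospitalized with COVID-19". Section P (Selection Bias) confirms that these are restricted populations: "Analyses that are restricted to people who received a positive test for SARS-CoV-2 or were hospitalised with COVID-19 may be vulnerable to selection bias".

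Section L defines the comparative cohorts relative to "a cohort entry date (1st March 2020 for wave 1, 1st September 2020 for wave 2), to make a total of four cohorts". No other entry date appears. The Censoring paragraph of the same section gives one exit rule, which differs between analyses only in the outcome: "For all cohorts, cohort exit will be defined as the first of either occurrence of the outcome", with death, leaving the practice, the end of data and the end of the wave as the alternatives.

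Section O gives one model statement for all outcomes: "using a Cox regression model to calculate hazard ratios and 95% CIs, using time in study as the time scale".

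Section N leaves exposure as either time-fixed or time-updated, to be decided after the descriptive study. The time-fixed form is "prescription of ICS within 3 months before the cohort entry date (1st March 2020 for wave 1, 1st September 2020 for wave 2" and is never updated. The exacerbation counts and the influenza and pneumococcal vaccination windows are also tied to cohort entry.

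**The concern.** A patient enters the 2b population only by testing positive, and the 2c population only by being admitted. Both events come after the wave start. If the clock runs from the wave start, membership is decided by a future event, and patients sit in the risk set during weeks or months when they have not reached the stage under study. The analysed time is then time to infection plus time from infection to admission (or the equivalent for death), so a difference between groups in when they were infected or tested leaks into a hazard ratio meant to describe progression.

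Each exposure option adds a problem. Time-fixed exposure describes prescribing before the wave start, not before the infection. Time-updated exposure censors patients who discontinue or move to a treatment outside the study, so on a wave-start clock a patient could be censored before the test that made them eligible.

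**Working it through.** **Plan's own figures.** Table 1 reproduces exactly from (1.960 + 0.842)² / (0.64 × 0.36 × ln(HR)²) events, divided by the outcome probability. At HR 1.1 this is 3,750.1 events, and at 0.05% it gives N = 7,500,266. Table 1 does not depend on time zero, so it has no bearing on this point. The protocol gives no test dates or admission risks; those used below are assumptions.

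**Dates (sections L and N).**
- Wave 1, 1 March to 31 August 2020: 183 days. Wave 2, 1 September 2020 to 30 April 2021: 241 days.
- Time-fixed status and baseline covariates can therefore be set up to 183 days (6 months) or 241 days (8 months) before a test.
- The earliest qualifying prescription can be 91 + 183 = 274 days old, or 92 + 241 = 333 days old. These are maxima, for a test on the last day of the wave.

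**Structure.** Let T be days from wave start to the positive test and Y days from wave start to admission or censoring. The wave-start model analyses Y; a model from the test analyses Y − T. No 2b event can be credited before T once the patient has been selected on a later test. The pre-test share of person-time is ΣT/ΣY; in patients with the event it is the mean of T/Y.

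**Simulated Cox models for 2b.** Assumptions: 64% on ICS (as in Table 1); test day normal with SD 25 and mean 45, 92 or 120 (wave 1) or 90 (wave 2); 10% or 30% admitted, all within 14 days of the test; follow-up to wave end; five repetitions of 6,000 patients per scenario. Both origins are fitted to the same simulated data, so the comparison between them is the informative part. Selected results:

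| Wave, mean test day | Admitted | True HR | ICS test timing | HR from wave start | HR from test | Difference |
|---|---|---|---|---|---|---|
| 1, day 45 | 10% | 1.0 | equal | 0.993 | 0.993 | 0% |
| 1, day 120 | 30% | 1.5 | equal | 1.490 | 1.494 | −0.3% |
| 1, day 45 | 10% | 1.0 | 10 days later | 0.965 | 0.978 | −1.3% |
| 2, day 90 | 30% | 1.0 | 10 days later | 0.967 | 1.005 | −3.8% |
| 1, day 120 | 30% | 1.5 | 10 days later | 1.386 | 1.497 | −7.4% |
| 1, day 120 | 30% | 1.5 | 10 days earlier | 1.511 | 1.441 | +4.9% |

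With equal timing, the pre-test share of all person-time runs from 26.6% (mean day 45) to 74.1% (mean day 120) in wave 1, and from 40% to 48% in wave 2. In patients with the event it is 82% to 95%.

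**Larger shift, higher risk.** With test day normal (mean 60, SD 30), mean lag to admission 5 days, true HR 1.0 and a 14-day difference in test timing, the wave-start HR is 0.95 to 1.04 at 30% admitted and 0.87 to 1.15 at 70%. A repeat run gave 0.94 to 1.03 and 0.87 to 1.16. From the test date the HR stays within 0.98 to 1.02. The effect grows with the admission risk because the group tested earlier is depleted first.

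**Time-fixed exposure.** If a share m of each group has changed ICS status by the test, the observed ratio is ((1 − m)HR + m) / ((1 − m) + m·HR). For HR 1.5:
- m = 10%: 1.45/1.05 = 1.38
- m = 20%: 1.40/1.10 = 1.27
- m = 30%: 1.35/1.15 = 1.17

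The protocol gives no value for m. Objective 2c has the same structure, with admission in place of the test; it was not simulated separately.

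**The case against.** The protocol never says in words that the 2b and 2c clock starts at the wave start. Time in study could be taken to begin at the test or admission, since section P speaks of selection into the study population through those events. Section N also lists calendar time as a covariate, which would be redundant if everyone entered on one date. This is a fair hint, but no statement supports that reading, it conflicts with the entry dates in section L, and exposure would still be anchored to the wave start under the time-fixed option.

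Fixed exposure is openly described as resembling intention to treat, and exposure misclassification is a planned bias analysis for 2a to 2c. That stands in part: section P attributes the misclassification to adherence and stockpiling, not to time elapsed before infection. The time-updated option, which section N prefers in theory, follows exposure to the end of follow-up with time-updated confounders, so out-of-date exposure is not a criticism of the plan as a whole.

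The analyses that do not condition on a test or admission avoid the problem, but they are additional analyses of a different question. The selection-bias correction in section P multiplies the estimate by a selection odds ratio and leaves time zero untouched.

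Re-anchoring has a risk of its own: an inhaler prescribed for early COVID-19 symptoms could be counted as prior exposure. The fix has to deal with that.

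**Conclusion.** The point holds and should be settled before analysis. The protocol defines one time zero, and it does not fit two of its three comparative objectives. Read as written, the plan counts selected, event-free time as time at risk and mixes infection timing with progression.

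The size is modest in most scenarios: about 1% with equal test timing; roughly 1–7% with a 10–14 day difference at 10–30% admitted; up to about 15% at an assumed 70% admitted. Timing differences and admission risks are assumptions. Section P does call unequal testing by ICS status plausible and describes wave 1 testing as very limited, so a difference cannot be set aside.

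Three stronger readings are tempting, and the documents do not support them.
- That the models analyse mostly pre-infection time: this is true of time to event in patients with the event, but across all person-time it depends on when tests fall.
- That exposure would be stale by the protocol's own 6-month rule: that rule, in the descriptive study, counts people with no ICS prescription for at least 6 months. The age of the qualifying prescription is a different quantity, and a patient with repeat prescriptions has not discontinued.
- That the study could not separate the stages of disease: the calculated shifts do not go that far.

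**What to change.** In sections L, N and O, give 2b and 2c their own index dates.

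- 2b: the first positive test. 2c: the COVID-19 admission. Start time in study there, and stratify by or adjust for calendar time.
- Assess ICS or comparator status and covariates from records before the index date, leaving out prescriptions issued for the acute illness, for example by a short lag.
- State how admissions on or before the test date are counted in 2b.
- State a follow-up window after the index date; its length is the study team's choice.
- Keep the wave start as time zero for 2a and for the analyses that do not condition on a test or admission.

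Delayed entry alone, on the wave-start clock with follow-up to wave end, is not a substitute. In the same simulations, with no true effect and a 10-day difference in test timing, it gave HRs of about 0.72 to 0.82 or 1.28 to 1.36, because patients long past their test stay in the risk set beside those just tested.

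The cost is protocol text and re-derived index-date variables from data already planned for extraction. Some patients will change exposure group or fall outside the exposure window.
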